10. RISKS TO SUBJECTS

- *Describe any potential risks which are not discussed in the protocol, their likelihood and seriousness. As a reminder, risks may be physical, psychological, social, legal or economic*
- *Discuss why the risks to subjects are reasonable in relation to the anticipated benefits and in relation to the importance of the knowledge that may reasonably be expected to result.*
- *Describe the procedures for protecting against or minimizing any potential risks, including risks to confidentiality, and assess their likely effectiveness.*

Undergoing two additional 15-lead ECGs may be physically uncomfortable for the patient because additional electrodes/stickers need to be placed on the subjects. Some patients report the leads are uncomfortable to remove as they require the small square of sticker/electrode. However, in order to minimize discomfort, we will be using the same electrodes/stickers placed on the patient for the standard 12-lead ECG. This means only 6 additional electrodes/stickers need to be placed on the patient.

There is only theoretical risk to privacy breach for patients in this study as we plan to use an encrypted and password protected database, REDCap, to collect and store all data. The paper data collection and consent forms will be stored in a locked cabinet in the AA office. Only IRB-approved study personnel will have access to data with PHI. In addition, all IRB-approved study personnel will have completed HIPAA training and are able to maintain patient confidentiality. All transmitted data will be sent over the secure Northwell Health network server.

11. RESEARCH RELATED HARM/INJURY

- *Describe the availability of medical or psychological resources that subjects might need as a result of anticipated problems that may be known to be associated with the research.*
- *If the research is greater than minimal risk, explain any medical treatments that are available if research-related injury occurs, who will provide it, what will be provided, and who will pay for it.*

When unconnected tips or electrodes from the ECG machine touch an item which is not equipotential grounded, the patient may receive an electrical shock. However, all of the study ED technicians performing the ECGs are trained and licensed ED technicians. Additionally, the technicians were provided additional study training specific to performing 15-lead ECGs on the Nihon Kohden machines.

12. PROVISIONS TO PROTECT PRIVACY INTERESTS OF SUBJECTS

- *Describe the methods used to identify potential research subjects, obtain consent and gather information about subjects to ensure that their privacy is not invaded.*
- *In addition consider privacy protections that may be needed due to communications with subjects (such as phone messages or mail).*

Patients will only be approached about the study in a private area. Information will be stored on paper files in a locked cabinet and on the encrypted REDCap database. No follow-up communication is required as a part of this study.

13. DATA AND SAFETY MONITORING

- *If not provided in the main protocol, please indicate here the plan to monitor the safety of this study.*
- *If the protocol has a data and safety monitoring plan, please indicate the page number on which the plan can be found.*

We do not anticipate any adverse events, but in the case of a study-related adverse event, in accordance with Northwell Health guidelines, the study team will alert the IRB of any and all reports of adverse events and inform all members of the study team of any and all reports of adverse events. If three or more adverse events are reported, the study team will assess potential causes of the adverse events and, if the events are clearly linked to study participation, discontinue the study.

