5. NUMBER OF SUBJECTS

- *Indicate the total number of subjects to be accrued locally. If applicable, distinguish between the number of subjects who are expected to be pre-screened, enrolled (consent obtained), randomized and complete the research procedures.*

The first phase of the study will be a pilot study, which will consist of enrolling 10 subjects to pilot test our data collection procedures and operations outlined in this protocol, as well as to troubleshoot issues that we did not expect. After our data collection procedures and operations are pilot-tested, the study will move onto the next phase for data collection.

The pilot study phase may take approximately two weeks to enroll 10 subjects. The main phase of the study will be the data collection phase, which is estimated to take 6 months. The data collection phase will consist of enrolling the remaining 290 subjects in the ED at NSUH or LIJMC.

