14. COSTS TO SUBJECTS

- *Describe any foreseeable costs that subjects may incur through participation in the research*
- *Indicate whether research procedures will be billed to insurance or paid for by the research study.*

This study is financed through a grant from Nihon Kohden. There is no foreseeable cost to subjects. Both of the 15-lead study ECGs will be performed on Nihon Kohden machines provided specifically for this study and will not be billed to the patient.

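### Section 13 requires a cause assessment only at three or more adverse events and states no cause review or equipment check after a first electrical shock or first serious study-related event

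*Combined protocol and SAP*

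**What the plan says.** Section 13 (Data and Safety Monitoring) anticipates no adverse events and then sets out two steps.

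- **Reporting.** The first step is notification: "the study team will alert the IRB of any and all reports of adverse events". Everyone on the team is informed as well. The scope of this step is given by its opening words, "in the case of a study-related adverse event, in accordance with Northwell Health guidelines".
- **Assessment and stopping.** The second step starts at a count: "If three or more adverse events are reported, the study team will assess potential causes of the adverse events". What follows the assessment is conditional on its result: "if the events are clearly linked to study participation, discontinue the study".

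The second step is a plain count. It does not grade events by seriousness or type, and the only action written after the assessment is discontinuation. No pause or equipment check is written at any count.

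Section 11 (Research Related Harm/Injury) names one specific hazard. If unconnected tips or electrodes "touch an item which is not equipotential grounded, the patient may receive an electrical shock". The safeguard offered is that the technicians are trained and licensed, and that "the technicians were provided additional study training specific to performing 15-lead ECGs" on the study machines.

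Two other places bear on the point. Section 14 says both study ECGs are "performed on Nihon Kohden machines provided specifically for this study". Section 5 describes a 10-patient pilot meant in part to "troubleshoot issues that we did not expect", followed by 290 further patients.

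**The concern.** The protocol identifies a hazard that arises from handling and grounding, and relies on training to prevent it. If a shock occurs anyway, either the safeguard has failed or the fault lies elsewhere, for example in the machine. Both can be checked straight away, and both could affect the next patient studied on the same equipment. A count of three suits minor, scattered events such as discomfort on removing electrodes. It fits poorly a single event that points to a correctable fault.

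At stake is the safety of the patients who follow a first shock or first serious event. Section 6 plans about 5 patients per day per hospital, or 50 per week over both. A first shock early in the day at one hospital could therefore be followed by up to 5 − 1 = 4 more study patients there that day. Section 13 states no check before them.

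**Working it through.** No computed figure stands behind the three-event threshold, so there is nothing to reproduce. The check is mainly a comparison of texts, followed by an illustration.

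**1. What is written for each event, by count**

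| Event | Written in section 13 |
|---|---|
| First or second, any severity | IRB alerted, study team informed |
| Third or later, any severity | As above, plus cause assessment; discontinue if clearly linked to participation |
| First shock | Same as any first event |
| First serious study-related event | Same as any first event |

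**2. Whether another section supplies the missing step**

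- Section 5: the pilot's troubleshooting aim could cover a shock among the first 10 patients. Nothing equivalent is written for the other 290.
- Section 6: the second hospital opens once the study runs well at the first. No safety criterion is given.
- Section 7, step 7: a research assistant is present during the ECGs, to collect the entry form.
- Section 9: the investigator meets staff regularly about data accuracy and protocol adherence. Safety review is not mentioned.
- Section 11: training and licensing only.

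None of these states a cause review, device check or pause after a single event.

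**3. Size of the threshold**

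Planned patients: 10 + 290 = 300 (section 5). Three events in three different patients is 3/300 = 1% of the study. Within the pilot it would be 3/10 = 30%.

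**4. Illustration, at assumed rates**

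The documents give no shock rate. Suppose shocks are the only adverse events and occur independently with probability r per patient, so that X ~ Binomial(300, r). Then

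- P(X ≥ 1) = 1 − (1 − r)^300
- P(X = 1 or 2) = P(X ≥ 1) − P(X ≥ 3)

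With r = 0.001, P(X ≥ 1) = 1 − 0.999^300 = 0.2593 and P(X ≥ 3) = 0.0036, so P(X = 1 or 2) = 0.2557. Differences below were taken before rounding.

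| Assumed r | P(at least 1) | P(at least 3) | P(1 or 2) |
|---|---|---|---|
| 0.01% | 0.0296 | <0.0001 | 0.0296 |
| 0.1% | 0.2593 | 0.0036 | 0.2557 |
| 0.2% | 0.4515 | 0.0230 | 0.4285 |
| 0.5% | 0.7777 | 0.1908 | 0.5869 |
| 1% | 0.9510 | 0.5779 | 0.3730 |

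The last column is the chance that the study has a shock but never reaches the written trigger. What the table shows is the pattern, not a level: if shocks are rare, nearly every study that has one ends below three. At r = 0.1% that share is 0.2557/0.2593 = 99%; at 0.5% it is 0.5869/0.7777 = 75%. At the lowest rate the study most likely sees no shock at all (1 − 0.0296 = 97%).

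**The case against.** The strongest reply is that a first event is not ignored and that part of the governing procedure is out of sight. Section 13 places the handling of study-related events under institutional guidelines that are not reproduced. Those guidelines, or the IRB once alerted, may require a review or suspension after one event. The term study-related also implies some judgement of cause at the first event, although no assessor or process is given. The three-event sentence leads into the stopping decision and can be read as an added escalation step. The study is two brief surface ECGs that reuse the electrodes already in place plus six more, with staff present and a staged start. All of this stands, and it keeps the point at low severity.

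It also rules out several stronger readings that a reader might infer:

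- *That nobody would look into a shock until the third event.* The documents do not say this. Nothing forbids earlier assessment; section 13 simply does not require it.
- *That no single-event review exists anywhere in the governing procedures.* This cannot be claimed without the guidelines.
- *That section 13 demands a documented assessment at three events but not at one.* It requires no written record at either count.
- *That unrelated events count towards the three.* The sentence carries no qualifier, but it follows one about study-related events and may share that scope. The gap at the first event is the same on either reading.
- *That the percentages above give the chance of an unexamined shock.* They give the chance that a count of three is not reached, at rates chosen for illustration.

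What the reply does not remove is the gap in the text: for a hazard that the protocol itself names, section 13 states no response beyond notification at its first occurrence.

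**Conclusion.** The point holds in a limited form. Section 13 ties cause assessment to three or more adverse events, without regard to severity and without a rule for the shock hazard in section 11. A first shock or first serious study-related event brings notification of the IRB and the study team, but no stated cause review or equipment check before the next patient.

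The conclusion rests on the protocol text alone and would fall away if the cited guidelines already require single-event review. Its size cannot be estimated from the documents, since they give no shock rate and anticipate no adverse events. It is worth acting on because the remedy is cheap, not because harm has been shown to be likely. It would be wrong to infer any weakness in the accuracy results, because sensitivity, specificity and the sample size do not depend on this rule.

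**What to change.** Add to section 13:

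> *After any single electrical shock or any serious study-related adverse event, study ECGs with the equipment involved will pause until the study team has assessed the cause (electrode and lead handling, grounding of nearby items, the machine) and either corrected it or, if no cause is found, had the machine checked or replaced and the investigator has agreed to resume.*

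The last clause supplies a release rule, so the pause cannot run on indefinitely when no cause is found. Keep the three-event sentence for other adverse events and for the discontinuation decision. If the institutional guidelines already require review after a single event, cite that requirement in section 13 instead.

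The cost is a one-sentence amendment and, only if such an event occurs, a possible short pause on the equipment involved. The number of machines per hospital is not given, so the effect of a pause on enrolment cannot be stated. Section 6 already allows for delays within the 6-month enrolment period. No data collection is added.

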14. COSTS TO SUBJECTS

- *Describe any foreseeable costs that subjects may incur through participation in the research*
- *Indicate whether research procedures will be billed to insurance or paid for by the research study.*

This study is financed through a grant from Nihon Kohden. There is no foreseeable cost to subjects. Both of the 15-lead study ECGs will be performed on Nihon Kohden machines provided specifically for this study and will not be billed to the patient.

15. PAYMENT TO SUBJECTS

- *Describe the amount of payment to subjects, in what form payment will be received and the timing of the payments.*

Subjects will not receive payment for participation.

16. CONSENT PROCESS

If obtaining consent for this study, describe:

- *Who will be obtaining consent*
- *Where consent will be obtained*
- *Any waiting period available between informing the prospective participant and obtaining consent*
- *Steps that will be taken to assure the participants' understanding*
- *Any tools that will be utilized during the consent process*
- *Information about how the consent will be documented in writing. If using a standard consent form, indicate such.*
- *Procedures for maintaining informed consent.*

Informed consent shall be obtained under the conditions set forth in 21 CFR Part 50: a)the subject shall have sufficient opportunity to consider participation in the study, b)informed consent shall be obtained without coercion or undue influence, c)informed consent shall be written in the native language of the subject and administered by approved personnel who speak the native language of the subject, d)a subject cannot be led to believe that they are waiving their rights as a subject or the liability of the sponsor or investigator.

If the patient qualifies, the Academic Associate will explain the study to the patient and summarize the consent form either in a private area of the waiting room or in a patient's room (depending on the time of identification). If the patient is interested, the Academic Associate will leave the patient with the consent form to read through and return 10 minutes later to see if they have any questions about the consent form or the study process. If the patient would like to move forward with enrollment, the AA will consent the patient using the standard consent form attached to this submission. A copy of the consent form will be given to the patient and the original will be kept in a binder in a locked cabinet in the AA office.

In the state of NY, any participants under the age of 18 are considered children. If your study involves children, additional information should be provided to describe:

- *How parental permission will be obtained*
- *From how many parents will parental permission be obtained*
- *Whether permission will be obtained from individuals other than parents, and if so, who will be allowed to provide permission. The process used to determine these individual's authority to consent for the child should be provided*
- *Whether or not assent will be obtained from the child*
- *How will assent be documented*
- *Whether child subjects may be expected to attain legal age to consent to the procedures for research prior to the completion of their participation in the research. If so, describe the process that will be used to obtain their legal consent to continue participation in the study. Indicate what will occur if consent is not obtained from the now-adult subjects.*

N/A

If the study involves cognitively impaired adults, additional information should be provided to describe:

- *The process to determine whether an individual is capable of consent*
- *Indicate who will make this assessment*
- *The plan should indicate that documentation of the determination and assessment will be placed in the medical record, when applicable, in addition to the research record.*
- *If permission of a legally authorized representative will be obtained,*
 - *list the individuals from who permission will be obtained in order of priority*
 - *Describe the process for assent of subjects; indicate whether assent will be required of all, some or none of the subjects. If some, which subjects will be required to assent and which will not.*
 - *If assent will not be obtained from some or all subjects, provide an explanation as to why not*
 - *Describe whether assent will be documented and the process to document assent*
 - *Indicate if the subject could regain capacity and at what point you would obtain their consent for continued participation in the study*

N/A

If the study will enroll non-English speaking subjects:

- *Indicate what language(s) other than English are understood by prospective subjects or representatives*
- *Indicate whether or not consent forms will be translated into a language other than English*
- *Describe the process to ensure that the oral and written information provided to those subjects will be in that language*
- *If non-English speaking subjects will be excluded, provide a justification for doing so*

N/A

17. WAIVER OR ALTERATION OF THE CONSENT PROCESS N/A

Complete this section if you are seeking an alteration or complete waiver of the consent process.

- *Describe the possible risks of harm to the subjects involved in this study and explain why the study involves no more than minimal risk to the subject:*
- *Explain why the waiver/ alteration will not adversely affect the rights and welfare of subjects*

- Explain why it is impracticable to conduct this research if informed consent is required
- If appropriate, explain how the subjects will be provided with additional pertinent information after participation. If not appropriate to do so, explain why.

N/A

Complete this section if you are obtaining informed consent but you are requesting a waiver of the documentation of consent (i.e., verbal consent will be obtained). To proceed with a waiver based on these criteria, each subject must be asked whether they wish to have documentation linking them to this study. Only complete subsection 1 OR subsection 2.

SUBSECTION 1

- Explain how the only record linking the subject to the research would be the consent document.
- Explain how the principal risk of this study would be the potential harm resulting from a breach in the confidentiality
- Indicate whether or not subjects will be provided with a written statement regarding the research.

N/A

SUBSECTION 2

- Describe the possible risks of harm to the subjects involved in this study and explain why the study involves no more than minimal risk.
- Confirm that the research only involves procedure for which consent is not normally required outside the research context.
- Indicate whether or not subjects will be provided with a written statement regarding the research.

N/A

18. WAIVER OF HIPAA AUTHORIZATION

N/A

Complete this section if you seek to obtain a full waiver of HIPAA authorization to use and/or disclose protected health information.

- Describe the risks to privacy involved in this study and explain why the study involves no more than minimal risk to privacy:
- Describe your plan to protect identifiers from improper use or disclosure and to destroy them at the earliest time.
- Indicate why it is not possible to seek subjects' authorization for use or disclosure of PHI.

- *Indicate why it is not possible to conduct this research without use or disclosure of the PHI.*
- *Indicate if PHI will be disclosed outside NSLIJ Health System, and if so, to whom. Note: PHI disclosed outside NSLIJ Health System, without HIPAA authorization needs to be tracked. Please see guidance at www.nslj.com/irb for information about tracking disclosures.*

N/A

Complete this section if you seek to obtain a partial waiver of the patient’s authorization for screening/recruitment purposes (i.e., the researcher does not have access to patient records as s/he is not part of the covered entity)

Note: Information collected through a partial waiver for recruitment cannot be shared or disclosed to any other person or entity.

- *Describe how data will be collected and used:*
- *Indicate why you need the PHI (e.g. PHI is required to determine eligibility, identifiers are necessary to contact the individual to discuss participation, other)*
- *Indicate why the research cannot practicably be conducted without the partial waiver (e.g. no access to medical records or contact information of the targeted population, no treating clinician to assist in recruitment of the study population, other)*

N/A

19. VULNERABLE POPULATIONS:

Indicate whether you will include any of these vulnerable populations. If indicated, submit the appropriate appendix to the IRB for review:

- Children or viable neonate*
- Cognitively impaired*
- Pregnant Women, Fetuses or neonates of uncertain viability or nonviable*
- Prisoners*
- NSLIJ Employees, residents, fellows, etc*
- poor/uninsured*
- Students*
- Minorities*
- Elderly*
- Healthy Controls*

If any of these populations are included in the study, describe additional safeguards that will be used to protect their rights and welfare.

N/A
